## D. STATISTICAL ANALYSIS PLAN

'Final Scores' determined from the score sheets will be compared between the 'operators' and 'clinicians'.

Mean scores of the two groups will be reported, with their respective standard deviations. Student's T-Test will be carried out to assess difference between the two groups. All hypothesis testing will be carried out using two-sided 5% significance level.

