## A. SPECIFIC AIMS

The aim of this study is to determine whether non-medical personnel, with no experience in ultrasound (US) use can effectively utilize the technology with remote guidance by expert assistance to assess for normal lung parenchyma among healthy volunteers.

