#### **B. BACKGROUND AND SIGNIFICANCE**

US has become an increasingly utilized modality in the healthcare setting. Advances in US technology and a burgeoning field of research showing its efficacy has rendered US a crucial tool in such fields as emergency and critical care medicine. The portability and ease of use of US has led to its use in the fields of wilderness, polar and aerospace medicine as well. Portable US machines have been taken on mountaineering expeditions and launched to the International Space Station, at which times it has been used to diagnose high altitude pulmonary edema and monitor intracranial pressure among astronauts, respectively (Wimalasena et al 2013, Lerner et al 2016). Emergencies in remote environments such as space may necessitate the use of US by non-medical personnel, at which time the data gathered would be transmitted to medical professionals to be analyzed and upon which clinical decisions would be made. Small studies have shown the effectiveness of utilizing non-medically trained personnel in obtaining adequate US images for such evaluations as optic nerve sheath diameter and carotid artery dynamics (Martin et al 2012).

Extreme environments such as space, expose those in it to such risks as depressurization, which can lead to multiple lung pathologies such as pulmonary edema and/or pneumothorax (Galdamez et al 2017). In such circumstances, remotely guided ultrasound may prove crucial to quickly identifying such medical complications of extreme environments. This initial pilot study will determine the feasibility of using remotely guided ultrasound among non-medical personnel on healthy volunteers to identify normal lung parenchyma by identifying commonly used indicators of such (e.g. lung-sliding, a-lines). If the results of the study indicate that such operations are feasible, further investigations into whether non-medical personnel are able to identify lung pathologies among confirmed cases of such conditions as pulmonary edema or pneumothorax may be pursued.

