#### C. RESEARCH DESIGN AND METHODS

#### 1. Rationale/overview

This study will assess the feasibility of remotely guided US use by individuals without ultrasound training to assess for normal lung parenchyma in healthy volunteers (patients) and amongst themselves. The untrained operators (operators) will perform US examinations of the lung under the guidance of a medical professional (expert) with experience in ultrasound technique. During the first portion of the study, the professional will guide the operator step by step on how to conduct an US exam of the 'patient's' lung. This simulation will be analogous to an untrained US operator assessing a potentially ill patient with the assistance of a remotely located physician.

The second portion of the study, during which time the participant will carry out an US exam on themselves, would be analogous to a lone patient in possession of US technology carrying out a self-examination under similar guidance of an expert. During both parts of the studye images will be saved and reviewed at a later time by an ultrasound expert to determine quality and clinical functionality in recognizing normal lung parenchyma. Images obtained by 'operators' will be compared against those obtained by US-trained clinicians (clinicians) captured from the same 'patient'. Real world examples of these scenarios would include an astronaut with respiratory distress after experiencing a rapid decompression event being evaluated by another healthy astronaut (or by themselves as in the second scenario) by US under the guidance of the flight surgeon at Mission Control.

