## 3. Study sample

A convenience sample of 20 healthy volunteers will be recruited from the Stony Brook undergraduate campus to participate as 'operators' in the study. 'Patients' will be recruited from a pool of standardized patient models who regularly participate in activities in the CSC. 10 US-trained clinicians will be recruited from SBU.

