## 5. Procedures

Volunteers will meet with study personnel in the CSC at SBU. Informed consent will be obtained from all groups ('operators', 'patients', 'clinicians'). A survey will be conducted to evaluate the subjects' prior experience in ultrasound. Subjects who qualify will continue to participate in the study.

The 'patient' will initially be evaluated by US by an expert and 'ideal' images will be captured and stored for later comparison against those obtained by 'operators'.

The 'operator' will be given an smart phone/table with video communication function and will be connected with the US 'expert', who will be located in a different room, physically and audibly out of range. For the first portion of the study, the 'expert' will instruct the 'operator' on how to conduct an US exam limited to the lung. Using the two-way video and audio communication through the video communication application, the expert will guide to the operator on how to utilize the US machine, where to place the probe, and how to capture and save images. The 'patient' will be instructed not to assist the 'operator' in any way. For the second portion of the study, the 'operator' will utilize the US machine to conduct a similarly limited lung exam on themselves, again with the assistance of the 'expert' but no other study personnel.

Finally, the 'clinicians' will carry out similarly limited lung exams on the 'patient', first without instruction from the 'expert' and then again under similar guidance as the previous portions of the study.

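### The only planned inference is a two-sided t-test for a difference between 20 operators and 10 clinicians, with no adequacy threshold, margin or confidence interval, so it cannot by itself answer the feasibility aim.

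*Combined protocol and SAP*

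**What the plan says.** Section A gives the aim: to "determine whether non-medical personnel, with no experience in ultrasound (US) use can effectively utilize the technology with remote guidance". Section B adds: "This initial pilot study will determine the feasibility of using remotely guided ultrasound among non-medical personnel". It links later work to the outcome: "If the results of the study indicate that such operations are feasible, further investigations" may follow.

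Section C.1 names the comparison: operators' images "will be compared against those obtained by US-trained clinicians (clinicians) captured from the same" patient. It also has an expert review saved images for quality and clinical usefulness. Section C.3 sets 20 operators and states "10 US-trained clinicians will be recruited from SBU".

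Under section C.5:
- An expert first captures ideal images of the patient for later comparison with the operators' images.
- Each operator scans the patient and then has to "conduct a similarly limited lung exam on themselves".
- Clinicians "will carry out similarly limited lung exams on the" patient, first unguided and then guided.
- Each exam is scored 0 to 6 by three experts, and their average is the Final Score. Higher is better; no value is called adequate.

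Section D is the whole analysis plan: group means, SDs, and "Student's T-Test will be carried out to assess difference between the two groups" at a two-sided 5% level.

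**The concern.** The aim asks whether operators do well enough; the test asks whether two group means differ. A non-significant result does not show that operators match clinicians, because a small study can miss a real deficit. A significant result does not show that operators are inadequate, because with little spread a trivial gap is enough.

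Section B makes further work depend on whether the results point to feasibility. If no score or margin is fixed beforehand, what counts as feasible is decided after the data are seen.

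**Working it through.** **Inputs.** From the documents: 20 operators and 10 clinicians (C.3), a Final Score from 0 to 6 (C.5), and a two-sided 5% Student's t-test (D). There is no power, SD, effect size or margin, so there is no figure of the plan's own to reproduce. Assumptions: one score per person, approximate normality and a common SD of 0.3 to 1.5 points.

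**Step 1: precision.** The standard error of the difference is SD × √(1/20 + 1/10) = 0.3873 SD. With 28 degrees of freedom the critical t is 2.048, so the 95% half-width is 2.048 × 0.3873 = 0.793 SD. With Welch at equal sample SDs (18.1 degrees of freedom) it is 0.813 SD. For the operator mean alone it is t(0.975, 19)/√20 = 0.468 SD.

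**Step 2: how often a real deficit is missed.** For a true 1-point deficit the noncentrality is 1/(0.3873 SD). The noncentral t distribution gives:

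| Assumed SD | Half-width, difference (points) | Half-width, operator mean (points) | True 1-point deficit non-significant |
|---|---|---|---|
| 0.3 | 0.24 | 0.14 | under 0.1% |
| 0.75 | 0.60 | 0.35 | 9% |
| 1.0 | 0.79 | 0.47 | 30% |
| 1.5 | 1.19 | 0.70 | 62% |

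**Step 3: a trivial gap that is significant (invented result).** Operators 5.60, clinicians 5.85, SD 0.3 in both groups. SE = 0.3 × 0.3873 = 0.116; t = -0.25/0.116 = -2.15; p = 0.040 (Welch 0.045). The interval for the difference is -0.49 to -0.01. The operator mean has interval 5.60 ± 0.14, or 5.46 to 5.74 out of 6. The p-value alone would look unfavourable; the operator interval shows scores close to the maximum.

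**Step 4: check without normality.** 100,000 trials were simulated with a capped six-item scorecard, true means 4.5 and 5.5, and SDs of about 1.2 and 0.7. The assumed inputs were beta-distributed item probabilities with intra-exam correlation 0.1, and three experts each scoring an item correctly 97% of the time. The planned test was non-significant in 32% of trials (Welch 22%). Step 2's result at SD 1.0 is therefore not an artefact of normality.

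**Step 5: search for a criterion.** Sections A to F contain no numeric threshold, margin or confidence interval. The ideal images and the review of clinical usefulness carry no scoring rule and do not reappear in section D.

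**The case against.** The strongest reply is that the plan is not without reference points. Clinicians are a stated comparator, so the t-test serves a declared purpose. Ideal images are stored, and the six scorecard items are meaningful in themselves: a reported operator mean of 5.6 out of 6 can be interpreted without any test. A reader could derive an interval from the means, SDs and group sizes. This is an unfunded convenience-sample pilot, and section B says only that further work may follow. All of that stands. It narrows the gap to the missing numeric criterion and the missing planned interval, but does not close it: nobody can derive from the report what score or gap the investigators held adequate beforehand.

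Three stronger readings are tempting and are not supported.

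- A reader might infer that the sponsor will treat non-significance as proof of feasibility. The documents do not say so; they give no basis for the conclusion either way.
- A reader might infer that the self-exam is left out of the comparison, or can be judged only against an absolute standard. Section D does not say which operator or clinician exam enters the test, and silence is not exclusion. All exams share one scale. Self-exam scores can be compared with clinicians' scores, but the comparison is confounded by subject because clinicians scan only the patient.
- A reader might infer that the test tends to point the wrong way, passing weak operators while flagging strong ones. Means of 4.5 and 5.5 with SD 1.5 in both groups do give p = 0.096. On a scale capped at 6, however, that SD implies an implausible clinician group: nine scores of 6 and one of 1 give mean 5.5 and SD 1.58. With SDs of 1.2 and 0.7, the pooled SD is √[(19 × 1.44 + 9 × 0.49)/28] = 1.065, t = -1/(1.065 × 0.3873) = -2.42 and p = 0.022. This is limited power, not systematic reversal.

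**Conclusion.** The concern holds in this limited form. The t-test informs the aim but cannot establish that operators are good enough or comparable, and the plan supplies nothing else that would. This should be fixed; it does not prevent the study from running.

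The size depends on an SD the documents do not give. The 30% miss rate belongs to an SD of 1.0 and a true 1-point deficit, and the p = 0.04 example to an SD of 0.3. The half-width of 0.79 SD needs only one score per person and the pooled analysis. The main conclusion depends on none of these values, since no SD supplies a standard of adequacy.

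**What to change.** In section D:

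1. Make estimation the main analysis. Report the operator mean Final Score with a 95% confidence interval, separately for the exam of the patient and the self-exam. Report the operator-minus-clinician difference with a two-sided 95% Welch interval, using the operators' exam of the patient and a named clinician exam (guided or unguided).
2. Before scores are seen, state one justified criterion and the interval to be read against it: either an adequate operator score or a margin for the difference. The value is for the sponsor to choose.
3. Keep the t-test as supportive, and state that a non-significant result will not be read as feasibility.

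The cost is a few lines of text and agreement on one criterion, with no added data collection. There are two downsides. With 20 and 10 participants the chosen interval may be inconclusive. The t interval for the operator mean may also be slightly too narrow near the ceiling: under the simulation's assumptions, coverage was 94% at a true mean of 4.5 and 91% at 5.5.

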During all portions of the study, time to image capture will be measured by observing personnel. All captured images will be sent to expert reviewers at which time a quality score will be generated. Ultrasound experts will blindly evaluate images obtained from both untrained and trained groups. Using the 'Ultrasound Quality Scorecard', evaluators will assess the quality of the image obtained and the technique carried out to obtain the image. These quality and technique criteria include 'Discernable Lung Parenchyma', 'Presence of A-lines', 'Lack of Obstruction from Rib Shadowing', 'Correct Probe Selection', Correct Depth Setting', 'Correct Gain Selection'. For each criterion (both quality and technique), a binary 'Yes/No' score will be given. Total 'Yes' scores will be summed for each ultrasound exam (minimum 0, maximum 6), with the higher number of 'Yes' responses signifying a higher quality ultrasound exam. Each ultrasound exam will be scored by three separate experts, with the average of the three scores being reported as the 'Final Score'. Reviewers will be comprised of three experts in the field of US, all MDs who have received formal training in US and have at least 5 years of clinical US practice experience. Each captured image will be reviewed and scored by all three reviewers.

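### Student's t-test with 20 operators and 10 clinicians is sensitive to unequal SDs; Welch's test on one named score per person is a cheap improvement

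*Combined protocol and SAP*

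**What the plan says.** Section D compares Final Scores between operators and clinicians at a two-sided 5% level: "Student's T-Test will be carried out to assess difference between the two groups". It also states "Mean scores of the two groups will be reported, with their respective standard deviations". It does not say whether the pooled or the unequal-variance form is meant, and it gives no planning SD.

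The group sizes come from section C.3: "A convenience sample of 20 healthy volunteers will be recruited from the Stony Brook undergraduate campus", and "10 US-trained clinicians will be recruited from SBU".

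The score is bounded and is defined per exam, not per person (section C.5): "Total 'Yes' scores will be summed for each ultrasound exam (minimum 0, maximum 6" and "Each ultrasound exam will be scored by three separate experts, with the average of the three scores being reported as the 'Final Score".

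Each person performs two exams. Operators first scan the patient; then "the 'operator' will utilize the US machine to conduct a similarly limited lung exam on themselves". Clinicians scan the patient twice, "first without instruction from the 'expert' and then again under similar guidance as the previous portions of the study".

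Section C.1 narrows the comparison. Operators' images are to be set against clinicians' images of the same patient, which points to the operator's patient exam rather than the self-exam. Nothing says which of the two clinician exams is used.

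**The concern.** The pooled test weights the two sample variances by their degrees of freedom, 19 and 9, so its standard error is driven by the larger group. When group sizes differ 2:1 and the SDs also differ, that standard error is wrong, and the direction depends on which group varies more:

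- If operators vary more, it is too large and power is lost.
- If clinicians vary more, it is too small and false positives rise.

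Unequal spread is plausible here. Untrained volunteers are compared with trained clinicians, whose scores may be compressed against the ceiling of 6. That remains an assumption.

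This t-test is the only inference in section D. Its error rates would rest on SDs unknown in advance, and choosing the form of the test after seeing them would be data-driven.

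**Working it through.** The plan gives no power, effect size or SD, so there is no figure of its own to reproduce. Group sizes, the 0-6 scale, the three raters and the two-sided 5% level come from the documents. All means, SDs, correlations and rater accuracies below are assumed. Results are Student / Welch.

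**1. Standard error of the difference, one score per person**

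Pooled SE = √{[(19·s₁² + 9·s₂²)/28] × (1/20 + 1/10)}; true SE = √(s₁²/20 + s₂²/10), with operators as group 1.

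- SDs 1.0/0.5: pooled √[(21.25/28) × 0.15] = 0.337; true √(0.050 + 0.025) = 0.274. The pooled SE is too large.
- SDs 0.5/1.0: pooled √[(13.75/28) × 0.15] = 0.271; true √(0.0125 + 0.100) = 0.335. The pooled SE is too small.

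**2. Normal scores, 20 vs 10 (100,000 simulated trials per row)**

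| Operator/clinician SD | Type I error | Power, 0.8-point deficit |
|---|---|---|
| 1.0/1.0 | 5.0% / 5.0% | 51% / 50% |
| 1.0/0.8 | 3.6% / 5.0% | 57% / 61% |
| 1.0/0.5 | 1.9% / 5.0% | 66% / 80% |
| 0.8/1.0 | 6.9% / 5.2% | – |
| 0.5/1.0 | 11.5% / 5.2% | – |

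With 15 vs 15, the pooled test's type I error is only 5.3% at an SD ratio of 2:1 and 5.6% at 3:1. The 2:1 group sizes therefore drive the problem. At equal SDs, with a larger difference, power is 77.0% / 75.1%.

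**3. Single binomial score, 0 to 6 (100,000 trials)**

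For a mean m, the SD is √[m(6 − m)/6]. At 5.2 and 5.7 this gives √0.693 = 0.83 and √0.285 = 0.53. At 3.0 and 4.0 it gives √1.5 = 1.22 and √1.333 = 1.15, which are nearly equal.

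| Operator vs clinician mean | Power | Gain (points) |
|---|---|---|
| 5.2 vs 5.7 | 37.4% / 50.2% | 12.8 |
| 5.0 vs 5.5 | 30.0% / 39.2% | 9.2 |
| 4.8 vs 5.5 | 50.3% / 59.4% | 9.1 |
| 4.5 vs 5.5 | 78.0% / 83.5% | 5.5 |
| 4.2 vs 5.0 | 46.8% / 51.8% | 5.0 |
| 3.0 vs 4.0 | 54.6% / 54.5% | none |

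The nominal range is thus 0 to 13 points. When both tests are adjusted to 5% size, the five scenarios with a gain keep 3 to 11 points.

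**4. Average of three raters, as the plan scores (40,000 trials, independent rater errors)**

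| Rater accuracy | 4.8 vs 5.5 | 5.2 vs 5.7 |
|---|---|---|
| 95% | 44.5% / 52.8% | 31.1% / 41.5% |
| 90% | 38.2% / 45.2% | 25.4% / 33.0% |

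The gains are about 7 to 10 points.

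**5. Confidence interval coverage, nominal 95% (single binomial score)**

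Operators 5.2, clinicians 5.7: 97.4% / 95.2%. Operators 5.5, clinicians 4.8: 91.5% / 94.6%.

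**6. More than one exam per person, type I error**

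- All exams, 40 vs 20, equal SDs: 8.6% / 8.5% at within-person correlation 0.3; 12.5% / 12.4% at 0.6.
- One operator exam and both clinician exams, 20 vs 20, SDs 0.5/1.0, correlation 0.3: about 8% with either test.
- Welch on each person's mean, 20 vs 10, correlations 0.3 and 0.6: 4.8% to 5.1%.

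**7. Welch near the ceiling**

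With single binomial scores and equal means, type I error is 4.5% / 6.3% at 5.7 and 3.9% / 7.0% at 5.8. A group of 10 clinicians has zero variance in about 5% and 13% of trials: (0.95⁶)¹⁰ = 0.046 and (0.967⁶)¹⁰ = 0.13. Using a permutation p-value only in zero-SD trials brings Welch's size to about 4.4% and 1.9%, with power of about 51% at 5.2 vs 5.7. With the three-rater average, Welch's size without any fallback is 5.0% to 5.5%.

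**The case against.** The strongest reply is that nothing in the plan is shown to be wrong. Reading the test as pooled is an inference from its name. The documents give no SDs, and with equal SDs Student's test is correct and slightly more powerful. The aim is feasibility, section B ties further work to the study's results rather than to this p-value, and group means and SDs will be published, so a reader could compute Welch's test. All of this stands, and it keeps the point minor.

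A second reply is that Welch is not exact either. That also stands: its size reaches 6% to 7% for single scores near the ceiling. In one bounded-score scenario with equal means and clinicians more variable (SDs 1.09 and 1.85), it was 6.5%, against 10.3% for the pooled test.

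Three stronger readings are tempting, and the documents do not support them:

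- *The trial's false-positive rate is inflated.* That needs clinicians to vary more. If the ceiling compresses clinicians' scores, the pooled test is conservative instead.
- *The plan leaves the choice of exam entirely open.* Section C.1 points to the operator's patient exam. What is missing is mainly the clinician exam.
- *Switching to Welch settles the analysis.* It does so only with one score per person. If both clinician exams enter, the groups become 20 vs 20 and Welch repairs almost nothing.

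**Conclusion.** The point holds as a low-cost improvement. If Student's test is run in its pooled form on one score per person, its behaviour depends on an SD ratio that the documents do not give. The two-fold SD differences behind the 1.9% and 11.5% error rates are illustrative, as are the means behind the power gains, and the three-rater gains also assume 90-95% independent rater accuracy. Operators varying more is the likelier case, so lost power is the more probable harm than false positives, but this too is a judgement.

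The consequence for the study is limited. A reader might take a non-significant result, especially from a conservative test, as showing that operators match clinicians. Neither test supports that conclusion.

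**What to change.** In section D:

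1. Replace Student's t-test with Welch's unequal-variance t-test, and report its 95% confidence interval for the mean difference.
2. Enter one Final Score per person. Confirm that the operator's score comes from the exam on the patient, and name the clinician exam (unguided or guided) it is compared with.
3. If more than one exam per person is analysed, use Welch on each person's mean, or a mixed model with a person effect and separate residual variances by group.
4. Use a permutation p-value for the Welch statistic only if a group has zero SD. Permuting in every trial is a different rule: its size falls to 1.7-3.7% at binomial means of 5.5 to 5.8, and its power at 5.2 vs 5.7 is about 40%, which loses most of the gain.

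The cost is a few sentences and one software option, with no change to design or recruitment. The statistical price is about 2 points of power if the SDs are equal. Near the ceiling, the zero-SD rule removes the excess in Welch's size for single scores with little loss of power, although the test then becomes conservative.
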